5.3 Study Procedures/Study Interventions

5.3.1 Study Visits- Cycle 1 Day 1 (may have been done within 5 days of treatment start/day 1, unless otherwise indicated as “same day”)

Subjects will return to the enrolling clinic at Day 1 of cycle 1 for evaluations. The following evaluations will be conducted prior to starting study drug:

1. Physical examination (including body weight) and medical history (**same day**);
2. Karnofsky Performance status/Lansky Play status-Appendix I (**same day**);
3. Vital signs, including height, weight, temperature, pulse rate, and sitting blood pressure (**same day**);
4. CBC with differential;
5. Serum electrolytes, BUN, creatinine, Bilirubin, ALT, AST;
6. LDH and/or Specific Tumor Markers for defined disease (if available);
7. Baseline EKG (as indicated);
8. Cycle 1 Day 1 Baseline Symptom Form (**same day**);
9. Review and recording of concomitant medications (**same day**);
10. Completion (by study staff) of Case Report Forms;
11. Any additional labs or testing required by the tumor board.

5.3.2 Study Visits- Cycle 1 Day 8 (\pm 3 days)

Subjects will return to the enrolling clinic at Day 8 of cycle 1 for evaluations. The following evaluations will be conducted at those time points:

1. Physical examination and medical history;
2. Vital signs, including height, weight, temperature, pulse rate, and sitting blood pressure;
3. CBC with differential;
4. Monitoring of AEs;
5. Review and recording of concomitant medications;
6. Completion (by study staff) of Case Report Forms;
7. Any additional labs or testing required by the tumor board.

5.3.3 Study Visits- Cycle 1 Day 15 (\pm 3 days)

Subjects will return to the enrolling clinic at Day 15 of cycle 1 for evaluations. The following evaluations will be conducted at those time points:

1. Physical exam and medical history;
2. Karnofsky Performance status/Lansky Play status-Appendix I;
3. Vital signs, including temperature, pulse rate, and blood pressure (sitting);
4. CBC with differential;
5. Serum electrolytes, BUN, creatinine, Bilirubin, ALT, AST;
6. Review and recording of concomitant medications;
7. Monitoring of AEs;
8. Completion (by study staff) of Case Report Forms;
9. Any additional labs or testing required by the tumor board.

5.3.4 Study Visits- Cycle 1 Day 22 (\pm 3 days)- for 28 day cycles only

Subjects will return to the enrolling clinic at Day 22 of cycle 1 for evaluations. The following evaluations will be conducted at those time points:

1. Physical examination and medical history;
2. Vital signs, including height, weight, temperature, pulse rate, and sitting blood pressure;
3. CBC with differential;
4. Monitoring of AEs;
5. Review and recording of concomitant medications;
6. Completion (by study staff) of Case Report Forms;
7. Any additional labs or testing required by the tumor board.

5.3.5 Subsequent Cycles (Maintenance Protocol Treatment Cycles) (up to 14 day window from end of previous cycle to start Day 1 of the next Cycle treatment per treating institutions standard of care)

Drug administration will be according to guidelines in previous cycles with dose modifications if needed per Section 5.1.1. The following evaluations will be performed on day 1 of each cycle as indicated. Evaluations may be performed within 5 days prior to dosing unless otherwise indicated. Subsequent cycles (cycles 2 and beyond) may be given at the subject's home institution. If subjects are to receive subsequent cycles at a home institution, this will occur only at COG (Children's Oncology Group) member hospitals or those specifically approved by the Site Principal Investigator.

1. Physical examination and medical history;
2. Karnofsky Performance status/Lansky Play status-Appendix I;
3. Vital signs, including height, weight, BSA, temperature, pulse rate, and sitting blood pressure (**same day**);
4. CBC with differential;
5. Serum electrolytes, BUN, creatinine, Bilirubin, ALT, AST;
6. LDH and/or Specific Tumor Markers for defined disease (if available);
7. Review and recording of concomitant medications;
8. Monitoring of AEs (must be done on Day 1);
9. Completion (by study staff) of Case Report Forms;
10. Any additional labs or testing required by the tumor board.

5.3.6 Reevaluation during Subsequent (Maintenance) Cycles

Subjects will be assessed for disease at the end of cycle 2 and every other cycle or every 8 weeks*, whichever occurs first, with the following (timing should be during the last week of the cycle):

1. CT or MRI of measurable disease sites (same scans as done at study entry);
2. MIBG/PET scan (if indicated for tumor type). Other imaging appropriate for tumor type may also be considered;
3. Any subject with suspected bone marrow disease and with positive bone marrow disease at study entry: Bone marrow aspirate and biopsy.

*After Cycle 6, reevaluations procedures in section 5.3.6 may be done per institutional standard.

5.3.7 Off Therapy/30 Day Follow-Up Visit

Subjects will be followed up at either the study clinic or by telephone within 30 (+7) days after the last dose of treatment. Last dose of treatment is defined as the last day that the subject received a tumor board recommended treatment. The following evaluations will be conducted:

1. Review and recording of concomitant medications;
2. Monitoring of AEs and review of concurrent illnesses;
3. Completion (by study staff) of Case Report Forms.

Any subject with suspected study drug related toxicities at the follow-up visit must be followed until all current drug related adverse events have resolved to baseline or \leq Grade 2 or stabilization of the event. This may require additional clinical assessments and laboratory

tests. The follow-up results will be recorded on the appropriate page of the CRF, as well as in the subject's source documentation.

6 Protocol Drugs

Specific treatment details will consist of a regimen chosen from a guided list of agents implicated in critical molecular signaling pathways and/or from signature-based predictions of drug efficacy summarized from the guided therapy report. All agents are listed in the current pharmacopoeia for human use, but will differ amongst individual subjects. The treatment regimens will be discussed with families and will include review of known side effects per Pharmacopeia Library (Appendix III) (information obtained from package insert and from MicroMedex, LexiComp, Facts and Comparisons, and Natural Medicines Database), serious adverse effects of possible new drug combinations, and any additional clinical monitoring that may be recommended by the tumor board. The family will be given the option to proceed with therapy and if the family decides to proceed with the tumor board's treatment decision they will be asked to sign a treatment specific memo.

Drugs will be prescribed by the enrolling institution per treating hospital protocol and administered per FDA guidelines and tumor board recommendations.

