13.7 Record Retention	60
References	61
Appendix I: Performance Status/Scores	64
Appendix II: Biology Studies Collection and Shipping forms	65
Appendix III: Pharmacopeia Library	67
Appendix IV- Example expression file format for the VCF 4.1:	69

PROTOCOL SYNOPSIS

PROTOCOL TITLE	Molecular-guided therapy for the treatment of patients with relapsed and refractory childhood cancers
PROTOCOL NUMBER	NMTRC009
PHASE OF DEVELOPMENT	Feasibility
OBJECTIVES	
Primary Determine feasibility of using tumor samples to assess genomic sequencing using predictive modeling to make real-time treatment decisions for children with relapsed/refractory cancers
 
Secondary
 
 • To determine the activity of treatments chosen based on: 
 • Overall response rate (ORR) • Progression free survival (PFS) • To continue to evaluate the safety of allowing a molecular tumor board to determine individualized treatment plans • (Voluntary) To explore the relationship between tumor phenotype/genotype and response by permitting use of tumor tissue in a correlative biologic study • To compare PFS interval to PFS intervals of previous chemotherapy regimens since relapse for each subject. • Sub analysis examination of disease types.
STUDY DESIGN	
A prospective open label, multicenter study to evaluate the feasibility of molecularly guided therapy in patients with relapsed or refractory childhood cancers
 
A total of 200 evaluable subjects with childhood cancer that are refractory to or have relapsed on conventional therapy will be treated with molecular guided therapy. Additional patients may enroll through compassionate access if no other treatment options are available.
 
Subjects will be evaluated in 3 strata:
 
 • Stratum 1: 50 subjects with refractory/relapsed neuroblastoma • Stratum 2: 50 subjects with relapsed or refractory brain tumors • Stratum 3: 100 subjects with refractory or relapsed rare tumors 
Guided therapy will allow the use of individualized therapeutic combinations (up to 4 agents). All subjects will be followed for survival, disease response, progression and safety. All subjects will be treated according to the discretion of the treating oncologist and study committee (minimum 3 oncologists and one pharmacist). Extent of disease will be measured and assessed for changes throughout the course of the study.

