7.1 Tumor Assessments/Scans

Tumor assessments/imaging studies must be obtained at baseline, at the end of cycle 2 and again after every other cycle (or every 8 weeks, whichever occurs first). After Cycle 6, may be done per institutional standard. The same method of assessment and the same technique should be used to characterize each identified and reported lesion at baseline and during follow-up.

All radiological images must be available for source verification. Images may be submitted for extramural review for final assessment of antitumor activity.

Subjects who come off study should have a final end of study disease-specific assessment done when possible.

7.2 Scan Submission:

All required study scans (CT's, MRI's, MIBG's and PET's) will be de-identified and sent to the NMTRC. All study required de-identified scans will be uploaded to HIPAA compliant database (if available) or sent on disc to:

[name]
NMTRC
Clinical Program Coordinator
[name]
[name]
[contact]
E-Mail: [contact]

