11 SUBJECT WITHDRAWAL AND TRIAL DISCONTINUATION

11.1 Criteria for Subject Off-Therapy

Subjects will be removed from the study therapy for the following reasons:

- Subject completes protocol defined therapy (a minimum of one cycle)
- Progressive neoplastic disease
- Subject or guardian withdraws consent to continue in the trial
- Subject develops an intercurrent illness that precludes further participation, or requires a prohibited concomitant treatment
- The Investigator withdraws the subject in the subject's best interests
- Subject is lost to follow-up (defined as the inability to contact the subject on 3 separate occasions over a period of 2 weeks)
- Administrative reasons (e.g., the subject is transferred to hospice care)
- An adverse event, which in the opinion of the Investigator, precludes further trial participation or fulfills the protocol requirements for withdrawal
- Death

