11.2 Criteria for Subject Off-Study

Subjects may be withdrawn from the study completely which includes withdrawal from survival follow-up for the following reasons:

- Completion of all study requirements
- Subject or guardian withdraws consent to continue in the trial (if this occurs, no further study visits or data may be collected)
- Subject is lost to follow-up (defined as the inability to contact the subject on 3 separate occasions over a period of 2 weeks)
- Death

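### No disease or survival follow-up is scheduled for subjects who stop therapy without progression, and no PFS event or censoring rule is written, so Kaplan-Meier PFS may be biased in either direction.

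*Combined protocol and SAP*

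**What the plan says.** The protocol speaks to follow-up after therapy in several places.

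- **Section 5.3.7** sets the only scheduled contact after treatment: "Subjects will be followed up at either the study clinic or by telephone within 30 (+7) days after the last dose of treatment". Its list covers concomitant medications, adverse events with concurrent illnesses, and case report forms. Only suspected drug-related toxicity extends it.
- **Section 5.3.6**, headed as applying to maintenance cycles, sets the scans: "Subjects will be assessed for disease at the end of cycle 2 and every other cycle or every 8 weeks*, whichever occurs first". They may follow institutional practice once cycle 6 is over. Section 7.1 repeats this.
- **Section 11.1** allows therapy to stop without progression. The reasons include "Subject completes protocol defined therapy (a minimum of one cycle") and "Administrative reasons (e.g., the subject is transferred to hospice care"), as well as adverse events, intercurrent illness, withdrawal of consent and investigator decision.
- **The synopsis** (Study Design) promises more: "All subjects will be followed for survival, disease response, progression and safety".
- **Section 7.1** adds: "Subjects who come off study should have a final end of study disease-specific assessment done when possible".
- **Section 11.2** separates leaving the study from leaving therapy: "Subjects may be withdrawn from the study completely which includes withdrawal from survival follow-up for the following reasons".

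Section 7.3 defines the measure under the PFS heading as time from first study drug to progression, without naming death as an event. Section 12.4 plans Kaplan-Meier plots by stratum and an exploratory Cox comparison with historical values. Neither section gives a censoring rule. Section 12.3 mentions censored data only for time to treatment start and time to completion of cycle 1.

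**The concern.** A site that follows Section 5.3.7 as written would not collect the dates of progression and death that the synopsis promises and the PFS analyses need. When the analysis is run, subjects who stopped without progression would most naturally be censored at or near stopping. Kaplan-Meier then assumes that their later risk equals that of subjects still on therapy. Hospice transfer makes that doubtful in one direction, and completed therapy in good condition makes it doubtful in the other.

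PFS is a secondary objective with several uses. The most exposed is the within-subject comparison with earlier regimens since relapse. Most tumor types must have relapsed or progressed to be eligible, so the earlier intervals will mostly end in an observed progression, while study intervals may end in censoring. Early stopping is a particular gap: the first scheduled on-study scan is at the end of cycle 2 or at 8 weeks, so a subject who stops after one cycle may have no scheduled scan after baseline. Dates not collected prospectively may be unrecoverable.

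**Working it through.** **The plan's own figures.** The documents give no median, event count, effect size or stopping rate for PFS. The only sizing is the feasibility design in Section 8 (5/9, then 10/16), and it reproduces. The chance of stopping at stage 1 under a 50% rate is (1+9+36+84+126+126)/512 = 382/512 = 0.746, as stated. Under 75% it is 0.166, as stated. Overall type I error is 0.088 and power 0.753. None of this bears on PFS.

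**Passages side by side.** The synopsis names survival and progression follow-up but gives no schedule, duration or end. Section 7.1 asks for one final assessment, without timing and only if feasible. Section 11.2 assumes survival follow-up and lists completion of all study requirements as a reason to leave, without defining it. Section 5.3.7 is the only one of these with a time and a list of items, and that list has no disease or vital status. The blank scan cells in the off-therapy column of the assessments table add little, because that table also omits the on-treatment scans that Section 5.3.6 requires.

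**Illustration of size. All inputs are assumptions.** Let h be the progression hazard on therapy, c the hazard of stopping without progression, and f = c/(h+c) the share who stop first, so c = h·f/(1−f). After stopping, the progression hazard is k·h. Set the true median to 3.0 months.

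- With censoring at stopping, Kaplan-Meier estimates exp(−ht), with median ln 2/h.
- The true curve is S(t) = exp(−(h+c)t) + [c/(h+c−kh)]·[exp(−kht) − exp(−(h+c)t)].

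With f = 0.4, k = 4, h = 1: c = 0.4/0.6 = 0.667 and S(t) = 1.286·exp(−1.667t) − 0.286·exp(−4t), which reaches 0.5 at t = 0.526. The ratio of estimated to true median is 0.693/0.526 = 1.317, and 3.0 × 1.317 = 3.95 months.

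With f = 0.4, k = 0.5, h = 1: S(t) = 0.429·exp(−1.667t) + 0.571·exp(−0.5t), which reaches 0.5 at t = 0.790. The ratio is 0.693/0.790 = 0.877, and 3.0 × 0.877 = 2.63 months.

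The same steps give the estimated median in months (true value 3.00):

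| Hazard after stopping, relative to on therapy | 10% stop | 20% | 30% | 40% |
|---|---|---|---|---|
| 0.5 | 2.94 | 2.86 | 2.76 | 2.63 |
| 1 | 3.00 | 3.00 | 3.00 | 3.00 |
| 2 | 3.09 | 3.19 | 3.31 | 3.45 |
| 4 | 3.19 | 3.40 | 3.65 | 3.95 |

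A simulation with 200,000 subjects per scenario agrees to about 0.01 month. At 30% stopping, 6-month PFS is estimated at about 0.29 against a true 0.23 when the later hazard doubles, and at about 0.22 against 0.28 when it halves.

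**The case against.** The strongest reply is that the protocol does not end disease follow-up at 30 days. Section 5.3.7 reads as a safety contact, the synopsis commits to following everyone for progression and survival, Section 7.1 asks for a final assessment, and Section 11.2 does not list stopping treatment as a reason to leave the study. This stands. A reader might infer that disease follow-up stops with the 30-day contact, but no passage says so. The fault is that the promised follow-up has no schedule, data items or end, and is not reconciled with Section 5.3.7.

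A reader might also infer that PFS is overstated. The documents do not support that. No censoring rule is written, so censoring at stopping is itself an inference, and the reasons in Section 11.1 include completed therapy as well as decline. A simple factor 1/(1−d) for a share d of events lost to censoring gives 1.18 at 15% and 1.43 at 30%, turning 3.0 months into 3.5-4.3. But it is the limit in which every censored subject would have progressed at that moment, and the 15-30% has no source in the documents.

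Nor does the comparison of the first and second 100 patients favor study therapy. Both cohorts receive it under one follow-up scheme, so that comparison suffers only if stopping patterns differ.

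Finally, PFS is secondary and the historical comparison is exploratory. That limits the importance of the point but does not remove it, because PFS serves several planned comparisons.

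**Conclusion.** The point holds as a gap in data collection and definition. The plan schedules no disease or vital status for subjects who stop without progression, and it does not define the PFS event and censoring rules. Bias in PFS by stratum and against prior regimens is possible, and its direction depends on why subjects stop. Its size cannot be computed from the documents. Under the assumptions above (constant hazards, true median 3.0 months, 10-40% stopping, censoring at stopping), the estimated median lies between about 12% too short and 32% too long, with no error when the hazard is unchanged. The primary feasibility endpoint is unaffected. The change should be made, because it is cheap and works whichever way the bias runs.

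**What to change.** 1. **Section 5.3.7, reconciled with the synopsis, 7.1 and 11.2.** For subjects off therapy without progression, record the date of progression from routine-care assessments, the start of any new anticancer therapy, and the date of death. Continue until progression, death or withdrawal of consent.
2. **Sections 7.3 and 12.4.** Make death without progression a PFS event and state the censoring rule. Without this, death dates collected under item 1 would conflict with the present definition in 7.3.
3. **Section 12.4.** Add a sensitivity analysis that counts stopping for decline, or starting new therapy, as an event.

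Section 8 says that 100 subjects had enrolled by Amendment 3.0. The same dates should therefore be sought for the first cohort as far as consent allows. Otherwise the change would itself create a difference in follow-up between the cohorts.

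The cost is a little coordinator time for periodic chart or telephone checks, plus short wording changes. No scans are mandated and no treatment rule changes.

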6.1 Treatment modifications

Dosing delays and modifications will be at the discretion of the treating Principal Investigator and their institutional pharmacist and based upon the selected therapy, subject response and practiced dosing regimens. Decisions will be made on the basis of clinical expertise of the physicians and pharmacists and with the subject's welfare being the principal concern. Informational websites such as drug bank (Micromedex, Lexicomp, Facts and Comparisons, Natural Medicines Database) will be utilized to identify potential adverse events associated with individual treatments. The study pharmacist will be available to consult on decisions made with respect to changes and modification made due to potential drug related adverse events.

6.2 Concomitant Medications and Treatments

All intercurrent medical conditions will be treated at the discretion of the Investigator according to acceptable community standards of medical care. All concomitant medications and treatments will be documented on the appropriate case report form.

The following medications are not permitted during the trial:

- Any cytotoxic chemotherapy
- Any other investigational treatment
- Any other systemic anti-neoplastic therapy including, but not limited to, immunotherapy, hormonal therapy, targeted therapies, anti-angiogenic therapies, or monoclonal antibody therapy

The following medications/treatments may be administered as follows:

- Any radiotherapy administered with palliative intent/pain control or recommended by tumor board as part of therapeutic regimen for best patient care.
- Prophylactic filgrastim, pegfilgrastim or oprelvekin; these hematopoietic growth factors may be administered according to ASCO, ASH, or institutional guidelines to treat an established cytopenia
 - If subject experiences a prolonged neutropenia greater than 72 hours during Cycle 1; consider using filgrastim or pegfilgrastim during all subsequent cycles.

- Erythropoietin, blood products, anti-emetics, steroids, and transfusions may be administered at the discretion of the Investigator based on established criteria.

7 Efficacy Assessments

